1.4. Description and justification of the therapeutic schema

The study drug is 2L[®]ALERG.

The treatment consists of taking one capsule a day, before breakfast, following the order of numbering: 1 through 10. When the number 10 has been taken, start another blister on the next day.

Method of administration: open the capsule, pour the contents (granules) under the tongue and let it dissolve. The pellets will be taken on an empty stomach, 15-30 minutes before the morning meal, or if taking has been forgotten, one hour after the meal.

The duration of treatment will be about 6 months.

2. Objectives and endpoints

2.1. Primary objective and primary endpoint

The main objective is to demonstrate the efficacy of 2L[®]ALERG versus placebo on the symptoms of allergic rhinitis and allergic rhino-conjunctivitis in patients with seasonal allergy to grass pollen.

The primary endpoint will be the area under the curve (AUC) of the overall score established according to the total 5 symptoms score (T5SS) and medication score (MS) according to time from the start of treatment until the end of the patient follow-up.

The five symptoms (sneezing, rhinorrhoea, nasal pruritus, eye itching and tearing, and nasal obstruction) will be assessed daily by patients on a scale from 0 (no symptoms) to 3 (severe symptoms) giving a total score ranging from 0 to 15.

The rescue medications (RM) allowed in the first-line adjuvant treatment will be codified to establish a score.

The allowed RM are the oral antihistamines (two points per day of use) or local treatment (nasal or eye; a point per day), and the ocular cromoglycate (one point per day).

In case of failure or in case of insufficiency of rescue medications mentioned above, the nasal topical corticosteroids (one point per day of use) will be allowed.

2.2. Secondary objectives and secondary endpoints

The secondary objectives will be to compare the effect of 2L®ALERG versus placebo on:

- Symptoms of allergy (not corrected by the use of rescue medication),
- Use of rescue medication,
- Evolution of the quality of life (QoL) using 3 daily specific questions included in the patient's diary card: Did you sleep well? Can you work normally? How do you feel?
- Safety (AEs and SAEs).

The secondary endpoints will be:

- Total 5 symptoms score (T5SS) and individual scores of 5 symptoms
- Consumption of rescue medications
- Evaluation of the QoL: AUC (total score of 3 questions of QoL included in the diary card on the Y-axis, and time on X axis) during the entire follow-up period
- Frequency, severity and causality relationship of AEs and SAEs.

[figure not shown]
3. Study design

3.1. Methodology

It is a double-blind, randomized, placebo-controlled, 2 parallel groups, interventional study, performed with a notified homeopathic medicine, available on the market since 2002.

3.2. Study design

- The study will last maximum 9 months: duration of inclusion = 1 month and patient's follow up = 6-8 months.
- The duration of 2L[®]ALERG exposure will be 6 months.

4. Study population

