Up Inclusion criteria	 Treatment set up two months before traditional pollen peak, then visits at 3 months and 6 months, or end of the peak. Age ≥18 years, male and female Woman of childbearing age using effective contraceptive means Patient having the faculties to understand and respect the constraints of the study Symptomatic since at least two seasons and confirmed by positive skin test and/or the presence of IgE for grasses (prick test defined as positive if higher than or equal to half the negative control; IgE positive if at least class 3 (≥ 3.5 kU / L); these tests must have been performed at the latest at the first screening visit Signature of the Informed Consent Form Pregnant woman or woman wishing to become pregnant Breastfeeding woman Patient with an acute exacerbation of allergic rhinitis Patient with uncontrolled asthma Immunotherapy received within the last two years

Version 1.0, 04 February 2016, Page 4

	 travel or to move before the end of the study, Patient taking nasal or bronchial inhaled corticosteroids on a long term basis (intermittent consumption during the season is permitted provided it is mentioned in the patient's records)
Primary endpoint	Area under the curve [AUC](total score of symptoms taking into account the Total 5 Symptom Score (T5SS) and consumption of rescue medications (RM) on the Y-axis, and time on X axis) during the entire follow-up period.
Secondary endpoints	 Total score on the T5SS scale and individual symptoms scores Frequency of daily RM consumption Evaluation of the quality of life: AUC (total score of 3 questions of quality of life included in the diary card on the Y-axis, and time on X axis) during the entire follow-up period Safety: adverse events (AEs) and serious adverse events (SAEs)
Sample size	A sample size of 32 patients in each group will have 90% power to detect a difference in means of 25 (the difference between a placebo group mean, μ 1, of 80 and a 2L [®] ALERG group mean, μ 2, of 55) assuming that the common standard deviation is 30 using a two group t-test with a 0.05 two-sided significance level.
	With a sample size of 43 patients in each group, the same assumptions are valid with a common standard deviation of 35.
	The final recommendation will be to include 50 patients per group in order to achieve at least 40 evaluable patients per group taking into account a potential drop-out rate of 20%.

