Study cohorts	 Two cohorts will be defined: Intention-to-treat (ITT) cohort including all patients having been exposed to at least one dose of the investigational product and in whom at least one efficacy or safety information has been collected after V0. Per protocol (PP) cohort including of the ITT having strictly adhered to the protocol and having a compliance between 80% and 120%. The primary cohort for the statistical analyses will be the ITT cohort. The patients who will prematurely stop the study will not be replaced.
Statistical analysis	A Statistical Analysis Plan (SAP) will be written by the Biostatistician of the CRO in charge of the study. This document will constitute the reference document as far as statistical analyses and statistical methodologies are concerned. It will be approved and signed by the Sponsor and the Principal Investigator before the last patient last visit at the latest. The objective will be to demonstrate the superiority of 2L [®] ALERG over placebo. This will be demonstrated using an independent Student's test comparing the over-time T5SS (corrected with RM) evolution (AUCs) of the two study groups, over the whole treatment period. A P value lower than 5% will be considered statistically significant.

ABBREVIATIONS

AE	Adverse Event
AFMPS	Agence Féderale des Médicaments et des Produits de Santé
AUC	Area Under the Curve
CD	Cluster Differentiation
СН	Centésimale Hahnemannienne
CRA	Clinical Research Associate
CRF	Case Report Form
CRO	Clinical Research Organization
GCP	Good Clinical Practice
GM-SF	Granulocyte-Macrophage-Stimulating Factor
HLA	Human Leukocyte Antigen
ICF	Inform Consent Form
ICH	International Conference on Harmonization
IgE	Immunoglobulin E
IL	Interleukin
ITT	Intention-To-Treat
MedDRA	Medical Dictionary for Regulatory Activities
PP	Per Protocol
RM	Rescue mediation
SAE	Serious Adverse Event
SAP	Statistical Analysis Plan
SAR	Serious Adverse Reaction
SmPC	Summary of Product Characteristics
SNA	Specific Nucleic Acid
SUSAR	Suspected Unexpected Serious Adverse Reaction
T5 SS	Total 5 Symptoms Score
Th	T helper
TNF	Tumour Necrosis Factor

Table of Contents

1.	BACKGROUND AND STUDY RATIONALE	9
1.1.	BACKGROUND	9
1.2.	STUDY RATIONALE	9
1.3.	BENEFITS AND RISKS FOR PEOPLE INVOLVED IN THE STUDY	14
1.4.	DESCRIPTION AND JUSTIFICATION OF THE THERAPEUTIC SCHEMA	14
2.	OBJECTIVES AND ENDPOINTS	15
2.1.	PRIMARY OBJECTIVE AND PRIMARY ENDPOINT	15
2.2.	SECONDARY OBJECTIVES AND SECONDARY ENDPOINTS	15
3.	STUDY DESIGN	16

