6.2. Study schedule

Study flow chart

	Screening (– 1 month)	V0 (2 months before grass pollen peak)	V1 (3 months after V0)	V2 (6 months after V0 or end of grass pollen peak)
Selection of patients Verification of inclusion/exclusion criteria Performance of allergy tests if needed	•			
Give information about the study Give the Inform Consent Form to the patient	•			
Eligibility check		•		
Signature of the Informed Consent Form		•		
Randomization		•		
Demography		•		
Medical history		•		
Physical examination		•	0	0
Allergy treatment history		•		
Delivery of treatment for 3 months		•	•	
Distribution of the patient diary		•	٠	
Start of treatment		•		
Diary card filling by the patient		•	•	•
Patient diary card control			•	•
Compliance control			•	•
Relevant (allergy-related) concomitant medications (except rescue medications)		•	•	•
Safety control (AE/SAE)			•	•
Study conclusion				•

• Compulsory • Optional

6.3. Identification of all the data sources that are not in the medical file

All data collected in the CRF have to be recorded in the patient medical file.

Patient diary data are source data which will be directly captured by the data management.

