A Statistical Analysis Plan (SAP) will be written by the Biostatistician of the CRO in charge of the study. This document will constitute the reference document as far as statistical analyses and statistical methodologies are concerned. It will be approved and signed by the Sponsor and the Principal Investigator before the last patient last visit at the latest.

Study cohorts

Two cohorts will be defined:

- Intention-to-treat (ITT) cohort including all patients having been exposed to at least one dose of the investigational product and in whom at least one efficacy or safety information has been collected after V0.
- Per protocol (PP) cohort including of the ITT having strictly adhered to the protocol and having a compliance between 80% and 120%.

The primary cohort for the statistical analyses will be the ITT cohort.

The patients who will prematurely stop the study will not be replaced.

Statistical methods

The IBM SPSS Statistics (Version 21.0 and eventual upgrades) software will be used throughout statistical analyses.

Missing values will not be replaced, nor extrapolated.

Classical descriptive statistics will be used to describe the patient population at baseline.

The two groups will be compared at baseline using independent Student's t tests for continuous variables and Mann-Whitney's tests, Chi-square tests or Fisher's exact tests for discrete variables.

The superiority of the active treatment over placebo will be demonstrated using an independent Student's test comparing the over-time T5SS (corrected with RM) evolution (AUCs) of the two study groups over the whole treatment period. A P value lower than 5% will be considered statistically significant.

The comparisons between the two study groups in terms of secondary endpoints will be done using the appropriate statistical methods, as they will be described in the SAP. No correction being applied for the multiplicity of endpoints, p values lower than 5% will be considered with caution, as indicative only of potential statistically significant differences between the two groups for the secondary endpoints.

8. Pharmacovigilance and management of adverse events

8.1.Definitions

Adverse events

An adverse event is defined as any untoward medical occurrence in a patient or a participant in a clinical trial, whether or not considered drug related.

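### The primary AUC is a total with no single fixed end, so a patient with a shorter diary scores a lower symptom burden

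*Protocol*

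**What the plan says.** **Endpoint definition.** Section 2.1 runs the AUC of the combined symptom and medication score "from the start of treatment until the end of the patient follow-up". The synopsis (Primary endpoint) says "during the entire follow-up period", and uses the same window for the quality-of-life AUC, as does section 2.2.

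**Primary test.** Section 7.2 (Statistical methods) specifies a Student's test "comparing the over-time T5SS (corrected with RM) evolution (AUCs) of the two study groups over the whole treatment period". The statistical analysis row of the synopsis matches it.

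**Lengths.** Section 3.2 gives "duration of inclusion = 1 month and patient's follow up = 6-8 months" and 6 months of exposure. The synopsis gives 6 months of treatment and follow-up of up to 8 months. Section 1.4 says about 6 months of treatment, and section 5.5 supplies drug for 3 + 3 months.

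**Last diary visit.** The flow chart in section 6.2 heads the final column "V2 (6 months after V0 or end of grass pollen peak", with V0 two months before the peak. The synopsis offers the same two alternatives. Diaries are handed out at V0 and V1, checked at V1 and V2, and the study concludes at V2.

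**Related rules.** Section 8.5 sets a two-month follow-up for adverse events after the end of the study. Section 7.2 rules out replacing or extrapolating missing values, takes the ITT cohort as primary and allows for 20% drop-out.

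**The concern.** Two different periods are named for one primary endpoint, and the visit that closes the diary has two possible dates. That would matter little for an average score. It matters for a total, because area accumulates with time: of two patients with the same daily severity, the one with fewer diary days has the smaller AUC and looks better.

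At stake are the meaning of the primary result (burden over which period?), some precision if diary length varies by chance, and the validity of the comparison if diary length differs between arms.

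**Working it through.** **1. The plan's own figures.** Inputs from section 7.2: means 80 and 55, difference 25, SD 30 or 35, two-sided alpha 0.05, power 90%. For a two-sample t-test with n per group, d = 25/SD, the noncentrality is d × √(n/2) and df = 2n − 2.
- SD 30: d = 0.833. With n = 32, the noncentrality is 0.833 × 4 = 3.33 and power is 90.7%.
- SD 35: d = 0.714. With n = 43, power is 90.6%.
- Drop-out: 40/(1 − 0.20) = 50 per group.

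All agree with the protocol, so this point does not rest on an error in the sample size.

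**2. Which windows can be computed?** The AUC needs diary scores, and no diary is issued for use after V2. If V2 is at month 6, follow-up with a diary and treatment cover the same V0-V2 span. The extra two months may be the adverse-event follow-up of section 8.5 (6 + 2 = 8). The protocol does not say so: section 8.5 places that period after the end of the study, whereas section 3.2 counts it inside the study (1 + 8 = 9 months at most).

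**3. How a total scales with length.** Assume a constant daily score and that 80 and 55 are 6-month values; the text of section 7.2 does not state the period they cover. Then AUC = 6-month value × months/6.

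| Window (months) | Placebo | Active | Difference |
|---|---|---|---|
| 4 (assumed) | 53.3 | 36.7 | 16.7 |
| 6 | 80 | 55 | 25 |
| 8 | 106.7 | 73.3 | 33.3 |

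Thus 8/6 = 1.33 and 6/4 = 1.5. An average placebo patient with a 4-month diary (53.3) scores about the same as an average active patient with 6 months (55).

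**4. Length varying by chance, the same in both arms.** Let AUC = R × L, where R has the planned mean μ and SD σ, and L is months/6, uniform and independent of R. Then Var(AUC) = (μ² + σ²)(Var L + (E L)²) − μ²(E L)².

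For 4-6 months, E L = 0.833 and Var L = (2/6)²/12 = 0.00926. The arm variances are 7300 × 0.7037 − 6400 × 0.6944 = 692.6 (placebo) and 3925 × 0.7037 − 3025 × 0.6944 = 661.3 (active). The pooled SD is 26.0, the difference 20.8 and d = 0.801.

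| Spread of length | d at SD 30 | Power, 40 per group |
|---|---|---|
| fixed | 0.833 | 95.7% |
| 4-6 months | 0.801 | 94.3% |
| 6-8 months | 0.816 | 95.0% |
| 4-8 months | 0.751 | 91.3% |

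At SD 35 with 40 per group, power falls from 88.4% (fixed) to 82.8% (4-8 months, the widest spread assumed).

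**5. Length differing by arm.** Illustration with no true effect: both arms have a full AUC of 80, patients who stop do so at month 3 with half of it (40), and their partial AUCs are analysed. Let 25% stop on placebo and 15% on active, which averages the planned 20%.
- Placebo: 0.75 × 80 + 0.25 × 40 = 70.
- Active: 0.85 × 80 + 0.15 × 40 = 74.

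A spurious difference of 4 appears in favour of the arm with more drop-outs, which is 4/25 = 16% of the planned effect. The split and the stopping time are assumptions.

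**The case against.** The strongest reply is that little turns on the wording. Diaries end at V2, so an 8-month AUC probably cannot be computed and the 33% describes no analysis that could be run. **This stands**, and the 6- versus 8-month conflict should be treated as mainly textual.

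Second, no 4-month window appears anywhere. Section 3.2 gives follow-up a floor of 6 months, section 4.3 excludes patients not motivated for at least that long, and drug is supplied for 6. **This stands too**: the 4-month bound is an assumption, although the flow chart leaves an earlier V2 possible.

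Third, the disease is seasonal. Days outside the season probably score near zero, so proportional scaling overstates the effect of moving V2. **This stands** for V2 timing. It does not help with drop-out: a patient who stops before the season loses most of the burden and contributes an AUC near zero.

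Fourth, a reader might infer that V2 timing itself biases the comparison. The documents do not support that. The two triggers are elapsed time and pollen, both external to the patient, and allocation is double-blind and 1:1 within centre.

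Fifth, the SAP may standardise the AUC. It may, and the absence of such detail is not held against the protocol. But the protocol itself names two windows and an open end, and under section 7.2 the SAP need only be signed by the last patient's last visit, when the V1 diaries would already be back.

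**Conclusion.** The point holds as a defect of definition that should be corrected. The protocol names two periods for one primary AUC and ties the last diary to a visit with two possible dates. The difference between 6 and 8 months is probably nominal. What remains is a total with no common end and no replacement of missing values, which credits shorter diaries with lower burden.

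The size depends on why lengths differ. If length is unrelated to arm, the loss is small: about one percentage point of power at SD 30 with 40 per group for a two-month spread, and about four for the assumed 4-8 month spread. The +33% and +50% changes are upper-end illustrations that need a constant daily score and, for the second, the assumed 4-month bound. Bias arises only if diary length differs by arm or depends on outcome. Drop-out is the plausible route: section 6.4 lists voluntary discontinuation and intake of a forbidden treatment among the reasons to stop, and the primary ITT cohort keeps patients with as little as one item of efficacy or safety information after V0. The documents do not show that such a difference would occur.

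**What to change.** - Choose one AUC window with the same start and end for every patient, either a fixed range of study days or fixed pollen-season dates. State it identically in the synopsis (follow-up, primary endpoint, quality-of-life and statistical analysis entries) and in sections 2.1, 2.2, 3.2, 6.2 and 7.2.
- Reconcile the two V2 alternatives in the synopsis and section 6.2, so that it is clear which governs.
- If time after V2 is for adverse-event follow-up only, say so and exclude it from the AUC.
- Analyse the AUC divided by the diary days observed within the window. This fits the average-score recommendation that section 7.2 itself cites. For patients with complete diaries it only rescales: dividing difference and SD by the same number leaves d = 25/30 = 0.833, so the sample size is unaffected.

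**Downside.** A per-day average treats unobserved days like observed ones, so a patient who stops before the season would get a falsely low value. Restrict the window to the season, or add a sensitivity analysis for early stoppers.

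**Cost.** Wording in about eight places, one division and possibly one sensitivity analysis. No extra patients, visits or data are needed.

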4.1. Description of the population

Hundred patients to achieve 80 completed cases (50 patients per group to achieve 40 completed cases).

4.2. Inclusion criteria

- Age ≥ 18 years, male and female
- Woman of childbearing age using effective contraceptive means
- Patient having the faculties to understand and respect the constraints of the study
- Symptomatic since at least two seasons and confirmed by positive skin test and/or the presence of IgE for grasses (prick test defined as positive if higher than or equal to half the negative control; IgE positive if at least class 3 (\geq 3.5 kU / L); these tests must have been performed at the latest at the first screening visit
- Signature of the Informed Consent Form

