Beside the mast cells, many other cells are involved in the pathogenesis of immediate hypersensitivity. Eosinophils (containing many mediators within their granules), basophils and neutrophils attracted on the site of the reaction through soluble mediators, perpetuate the lesions. The role of basophils may be dominant in the orientation Th2 immune responses on contact with the allergen.

Genetic factors are important, in fact, several susceptibility genes have been associated with allergic diseases:

- HLA molecules (ensuring the presentation of allergens to CD4 lymphocytes)
- B chain for the high-affinity receptor for IgE (Fc \in RI β)
- IL-4
- Receiver beta adrenergic
- TNF
- CD14 (co-receptor lipopolysaccharide)

Genetic changes may explain the increase in allergies in recent decades, however, it is now recognized that gene transcription is modulated by the environment (defining "epigenetic").

Let's now see how the 2L[®]ALERG, Micro-Immunotherapy medication, can act:

Micro-Immunotherapy is based on the use of endogenous molecules obtained by biotechnological synthesis and administered in very low doses sublingually. These physiological mediators aim to restore the balance Th1/Th2 ^[27] without focusing on the causative agent of the disease.

Composition of 2LALERG[®]:

composition of L indhite .	
Interleukin 1	17 CH
Interleukin 4	17–27 CH
Interleukin 5	17 CH
Interleukin 6	17 CH
Interleukin 10	17 CH
Interleukin 12	9 CH
Interleukin 13	17 CH
Tumor Necrosis Factor Alpha	17 CH
Transforming Growth Factor Beta	5 CH
Pulmo histaminum	15 CH
SNA-HLA-II	18 CH

According to the law of Arndt-Schultz, high dilutions are used to obtain a braking effect, average dilutions, a modulating effect, and low dilutions, a stimulating effect.

IL-1 is in high dilution to slow down the activity of B and T lymphocytes, protein production and the acute phase of inflammation, and IL6 production by Th2 ^[27-29].

IL-4 is in high dilution to reduce Th2 differentiation ^[30] and to brake IgE synthesis.

IL-5 is high dilution to slow activation and proliferation of eosinophils and thus prevents the influx into the airways.

IL-6 is in high dilution to slow the inflammatory Th2 response [31] under the influence of IL-1. **IL-10** is in high dilution to reduce the stimulatory effects of IL-4 [32].

IL-13 is in high dilution to decrease the expression of HLA class II molecules on macrophages and to brake the production of IgE $[^{33}]$, which reduces the allergic reaction.

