6.1. Study procedures

The following demographic data will be collected during the first visit: date of birth, gender, ethnic group, weight, height, smoking habits and alcohol use status.

Medical history, treatment history, concomitant treatments and patient's physical examination will also be documented during V0.

The allergy must be confirmed by positive skin test and/or the presence of IgE for grasses (prick test defined as positive if higher than or equal to half the negative control; IgE are positive if at least class 3 (\geq 3.5 kU/L); these tests must have been made at the latest during the first visit.

A patient diary will be given to each patient.

- For evaluation of the total 5 symptoms score T5SS and rescue medication RS, it is essential that patients note **every day** the symptoms (sneezing, rhinorrhoea, nasal pruritus, itching and/or eye tearing and nasal obstruction) intensity, and the rescue medications, in their patient diary.
- It is also essential that the patient takes note **every day** of his/her QoL by filling in three questions included in his/her diary card: Did you sleep well? Can you work normally? How do you feel?
- It is also imperative that patients note the date of the start of treatment and the date of onset of symptoms.

This patient diary will be given to the patient at each visit, and will be brought back at the next visit, it will be reviewed and validated by the investigator and will be part of the CRF (Case Report Form).

All relevant (related to allergy) concomitant medications (except rescue medications) taken by the patient during the study period will be recorded at each visit in the CRF.

The AEs and SAEs will be recorded at V1 and V2 in order to assess safety.

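### The prick-test entry rule accepts a grass site that reacts no more than the negative control, so it does not confirm grass sensitisation

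*Protocol*

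**What the plan says.** Protocol section 4.2 (Inclusion criteria) asks for two things together: a clinical history ("Symptomatic since at least two seasons") and an objective test ("confirmed by positive skin test and/or the presence of IgE for grasses"). Each test has its own threshold. For the blood test it is "IgE positive if at least class 3", given as 3.5 kU/L or more. For the skin test it is "prick test defined as positive if higher than or equal to half the negative control".

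Section 6.1 (Study procedures) repeats the skin-test threshold in the same words and makes its purpose plain: "The allergy must be confirmed by positive skin test and/or the presence of IgE for grasses". The synopsis carries the same definition. The flow chart in section 6.2 lists, at screening, "Performance of allergy tests if needed", so results obtained before the study can be used for entry.

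Section 2.1 states the primary objective for symptoms "in patients with seasonal allergy to grass pollen".

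**The concern.** A negative control shows how much the skin reacts when no allergen is applied. A threshold set at half of that reaction lies below the background level, so meeting it says nothing about grass. Nowhere does the protocol add a positive control, a minimum wheal or a requirement to exceed the negative control.

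The IgE criterion does not repair this, because either test is enough. The two routes are also very uneven: IgE must reach class 3, while the skin test can be passed by an unreactive site.

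The objective names patients allergic to grass pollen, and this is one of only two objective confirmations of that allergy. Up to 20 general practices would apply the rule. Sites that follow it literally can enrol symptomatic patients who are not sensitised to grass. Sites that quietly substitute their own threshold depart from the written criterion, each in its own way. The per-protocol cohort, defined in section 7.2 by strict adherence to the protocol, inherits the faulty definition.

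**Working it through.** **Step 1: the rule itself.** Let W be the reaction at the grass site and N the reaction at the negative control. As written in 4.2, 6.1 and the synopsis, the test is positive if W ≥ 0.5 × N.

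| N (mm) | Threshold 0.5 × N (mm) | W = N | W = N/2 | W = 0 |
|---|---|---|---|---|
| 0 | 0 | passes | passes | passes |
| 1 | 0.5 | passes | passes | fails |
| 2 | 1 | passes | passes | fails |
| 3 | 1.5 | passes | passes | fails |

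The wheal sizes are examples; the first two result columns hold for any N, since N ≥ 0.5N whenever N ≥ 0. The rule rejects only a grass reaction smaller than half of a measurable negative control, for example 0 mm against 2 mm.

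**Step 2: who can enter because of it.** A patient is affected only if all of these hold: symptomatic for at least two seasons, qualified by prick test, no IgE of 3.5 kU/L or more, and not truly sensitised to grass. The protocol does not say how many such patients there would be.

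**Step 3: the plan's own sample size (section 7.2).** Inputs: difference 80 − 55 = 25, two-sided α = 0.05, power 90%. With the two-sample t-test and the noncentral t distribution, the required n per group for SD 20, 25, 30, 35 and 40 is 15, 23, 32, 43 and 55. All five match the protocol's table. Enrolment also agrees: 40 / (1 − 0.20) = 50 per group.

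**Step 4: illustration of dilution.** Assume a share p of such patients in each arm who lose a fraction L of the effect. The expected difference is then 25 × (1 − p × L), and the noncentrality is that difference divided by SD × √(2/n). Both p and L are assumptions. With n = 40 per arm:

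- L = 1 (no effect in these patients): the difference is 25 × 0.9 = 22.5 at p = 10% and 25 × 0.8 = 20 at p = 20%.
- L = 0.5 (half the effect kept): the difference is 25 × 0.95 = 23.75 and 25 × 0.9 = 22.5.
- L = 1 with a wider active arm: the active-arm variance becomes SD² + p(1 − p) × 25². At SD 30 and p = 10% this is 900 + 0.09 × 625 = 956.25, an SD of 30.92. The other active-arm SDs are 31.62 (SD 30, 20%), 35.79 (SD 35, 10%) and 36.40 (SD 35, 20%).

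| Power, 40 per arm | SD 30, p = 10% | SD 30, p = 20% | SD 35, p = 10% | SD 35, p = 20% |
|---|---|---|---|---|
| No effect, SD unchanged | 91.2% | 83.8% | 81.0% | 71.4% |
| No effect, active SD widened | 90.4% | 81.8% | 80.2% | 69.6% |
| Half effect kept, SD unchanged | 93.8% | 91.2% | 85.0% | 81.0% |

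With p = 0 the power is 95.7% at SD 30 and 88.4% at SD 35. With no effect in these patients and SD unchanged, power drops below 80% only when p exceeds about 24% (SD 30) or 11% (SD 35).

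**The case against.** The text and the arithmetic of the rule are hard to dispute, so the case against concerns weight.

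- **Few patients may be affected.** Four conditions must coincide, the symptom history stays mandatory, and the IgE route is sound. This stands: the size of the group is unknown.
- **It may be a slip of the pen.** A rule that calls no reaction positive contradicts the aim of confirming allergy so plainly that a wording error is plausible, and the 0 mm case is an extreme literal reading. That may be so, but the words appear three times and the protocol never shows which reference was meant. A site has nothing else to follow.
- **The power figures lean pessimistic.** The shares of 10% and 20% have no anchor in the protocol. The intention-to-treat cohort could hold between 40 and 50 per arm. At 50 per arm, with no effect in these patients and SD unchanged, power is 96.0% and 91.0% at SD 30, and 88.9% and 80.8% at SD 35. Section 1.2 also describes an action "without focusing on the causative agent of the disease", so a complete loss of effect in unsensitised patients is not a given. All of this stands, and the power figures should be read as illustration only.

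None of it makes the definition do its job. Nor can it wait for an analysis plan, since eligibility is fixed in the protocol and applied before randomisation.

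**Conclusion.** The concern holds and the definition must be corrected. As written, the skin-test route accepts patients whose grass site reacts no more than the negative control, and no other criterion makes up for it. This follows from the rule alone and needs no outside source.

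The consequence is limited in kind. Unsensitised patients would be randomised to both arms, so the comparison is not biased and type I error is unaffected. What suffers is the match between the patients studied and the stated objective and, possibly, the size of the effect. Its extent depends on a share of patients that the protocol does not give and on how much effect those patients would lose. The case for correction rests on a key entry criterion failing its stated purpose, not on a computed loss of power.

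**What to change.** The sponsor and the medical advisor should state which reference control or margin was intended, in a form under which a grass site reacting no more than the negative control cannot be positive. The choice of threshold is theirs. That single definition should replace the present wording in the synopsis, 4.2 and 6.1, and should also apply to earlier prick results used for entry.

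The cost is a wording correction in three places and in the sites' eligibility check, and possibly a few more screening failures. The sample-size calculation need not change.
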